## 6.5 Pre-specified Subgroup Analysis

### Primary outcome

Subgroup analyses to examine the role of age group, location of treating centre, known family history of DD, and alcohol intake upon the effect of the primary outcome (nodule hardness at 12-months post-first injection) will be performed. This analysis will be carried out using adjusted ANCOVA, including age and centre. For these analyses, age will be categorised into two groups of 18 to 49 years and 50 years or older, and alcohol intake will be categorised into four groups of non-drinker, up to 14 units/week, 14 to 35 units/week and more than 35 units per week. Treating centre location will also be categorised into two groups, defined as UK-based centres (Oxford and Edinburgh) and non-UK based centres (Groningen). Comparisons will be using a 2-sided significance level of 5% and 95% confidence intervals, and results will be tabulated as per the primary outcome adjusted ANCOVA and presented by strata using Forest plots.

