## 20. OUTCOME MEASURES ANALYSIS

### 20.1 Primary outcome

**Table 19:** Nodule hardness ANCOVA and linear mixed-effects regression results for all follow-up time-points

	Saline			Adalimumab			Treatment effect			
	N =	n	Mean change	N =	n	Mean change	SD	Mean difference	95% confidence interval	P-value
ANCOVA a										
12 months										
Adjusted ANCOVA b										
12 months										
Mixed effects regression b										
Baseline										
3 months										
6 months										

Repurposing anti-TNF for treating Dupuytren's disease (funded by Health Innovation Challenge Fund, Wellcome Trust)  
EudraCT Number: 2015-001780-40 and OCTRU Reference Number CTU0028

	Saline N =			Adalimumab N =			Treatment effect N =		
	n	Mean change	SD	n	Mean change	SD	Mean difference	95% confidence interval	P-value
12 months c									
18 months									

a nodule hardness and treatment arm | b nodule hardness, treatment arm, age group and centre | c primary endpoint

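### SAP 6.5 specifies no treatment-by-subgroup interaction test, so the subgroup plan as worded does not test whether the treatment effect differs between subgroups.

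*SAP*

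**What the plan says.** SAP 6.5 (Pre-specified Subgroup Analysis, Primary outcome) names four factors: age group, location of treating centre, "known family history of DD, and alcohol intake".

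- **Model:** "This analysis will be carried out using adjusted ANCOVA, including age and centre".
- **Levels:** "age will be categorised into two groups of 18 to 49 years and 50 years or older". "Treating centre location will also be categorised into two groups", UK and non-UK. Alcohol has four bands. Family history is given no levels.
- **Testing:** "Comparisons will be using a 2-sided significance level of 5% and 95% confidence intervals".
- **Reporting:** "results will be tabulated as per the primary outcome adjusted ANCOVA and presented by strata using Forest plots".

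The reporting template is Table 19 in SAP section 20.1, "Nodule hardness ANCOVA and linear mixed-effects regression results for all follow-up time-points". Its treatment-effect columns are mean difference, 95% confidence interval and P-value. The footnote to its adjusted models lists nodule hardness, treatment arm, age group and centre, with no product term.

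Only two interactions are named anywhere: time by baseline measurement (protocol 11.2, SAP 3.7) and treatment by time for secondary outcomes (SAP 6.3). SAP 4.1 attaches no multiplicity rule to subgroups and keeps its exploratory label for other outcomes. The 1% level and cautious reading in SAP 6.6 cover unplanned analyses only.

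**The concern.** The stated aim is about effect modification, and the SAP 1.2 change log gives the same motive: possible differences between the UK and the Netherlands and between age groups. That question is answered by comparing effects across strata, that is, by an interaction. Separate treatment tests answer another question. A significant result in one stratum beside a non-significant one in another often reflects only stratum size.

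The risk runs both ways. An ineffective drug may appear to work in one subgroup, and a drug that works equally in everyone may appear not to work in some. SAP section 7 also has an independent statistician repeat the SAP analyses of the primary outcome. If an interaction test was intended, it could not be reproduced from the present text.

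**Working it through.** **1. The plan's own figure.** SAP 3.3 uses effect size 0.62, two-sided 5%, 90% power and 20% loss. Per arm, 2 × (1.960 + 1.282)² / 0.62² = 54.7, so 55. Then 55 / 0.8 = 68.75, so 69 per arm and 138 in total, as stated. The documents give no error rate or power for the subgroups.

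**2. Numbers analysed.** 138 × 0.8 ≈ 110. Protocol section 6 allows up to 200, and 200 × 0.8 = 160.

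**3. Number of comparisons.** 2 + 2 + 2 + 4 = 10 strata (family history taken as yes/no).

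**4. No true effect.** If the ten tests were independent, 1 − 0.95¹⁰ = 40.1%. They are not, because each factor re-cuts the same patients. Simulation gives 31–35% for at least one significant stratum. This hardly moves with numbers analysed, stratum shares, or whether the tests adjust for baseline.

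**5. Why a uniform effect looks uneven.** With SD 8 and 1:1 allocation, the standard error in a stratum of n is 16/√n. Power for a 5-unit effect is Φ(5√n/16 − 1.96), before any gain from baseline adjustment. At 110 analysed:
- equal halves (n = 55): 64% in each;
- a 20/80 split (n = 22 and 88): 31% and 83%.

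**6. Uniform 5-unit effect, within-stratum ANCOVA (simulated).** Assumed unequal shares: 25/75, 30/70, 45/55, and 15/50/25/10 for alcohol.

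| Analysed | Strata | Baseline correlation | Some factor mixed* | Three binary factors only |
|---|---|---|---|---|
| 110 | unequal | 0.6 | 98% | 73% |
| 110 | equal | 0.6 | 94% | 53% |
| 160 | equal | 0.6 | 82% | 28% |
| 160 | equal | 0.8 | 46% | 3% |

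*A significant stratum beside a non-significant one in the same factor.

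Repeated runs move these figures by a few points. Alcohol alone gives 46–95% over the settings tried. Its assumed 10% band holds about 11 people at 110 analysed and would usually be non-significant under any plan.

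**7. Interaction tests instead.** Four tests at 5% give 1 − 0.95⁴ = 18.5% for at least one false signal; simulation gives 17–19%, whether the true effect is zero or a uniform 5 units. For two strata with shares p and 1 − p, the standard error of the difference in effects is (16/√N) × √(1/p + 1/(1 − p)). At N = 110:
- equal halves: 1.526 × 2 = 3.05, power Φ(5/3.05 − 1.96) = 37%;
- 20/80 split: 1.526 × 2.5 = 3.81, power Φ(5/3.81 − 1.96) = 26%.

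These use SD 8 with no credit for baseline adjustment. At correlation 0.6 the residual SD is 8 × √(1 − 0.36) = 6.4. The standard errors become 2.44 and 3.05, and the powers 54% and 37%.

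**The case against.** - **The text never says outright that treatment is tested against placebo within each stratum.** True: the word for the comparisons is left undefined, and a forest plot by strata is also the usual display for interaction results. A reader might infer that the SAP states a wrong method; it does not go that far. But 5% comparisons, tabulated like a table of mean differences with P-values and "presented by strata using Forest plots", most naturally mean stratum tests. On either reading no interaction test is specified.
- **The headline figure depends on assumptions.** This stands. The mixed pattern is near-certain only under some settings and comes mainly from alcohol, so a range is the honest statement.
- **A mixed pattern is not a false claim.** Also fair: no SAP rule treats it as evidence of heterogeneity. But the plan offers the reader nothing else by which to judge heterogeneity.
- **The remedy is imperfect.** Confidence intervals still show which strata cross zero, four interaction tests still carry about 18% error, and power is low. These are reasons to disclose the limits and label the results exploratory, not to keep stratum p-values.
- **The exposure is limited.** The factors are few, pre-specified and tied to the primary outcome, and age and centre are stratification factors. This keeps the matter one of interpretation.

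**Conclusion.** The point holds as a gap in method: SAP 6.5 asks whether four factors modify the treatment effect and specifies no test of that. Read naturally, it gives ten stratum tests at 5%.

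With no true effect, the chance of at least one significant stratum is 31–35%. With a uniform 5-unit effect, the chance of a mixed pattern in some factor is about 46–98% (110–160 analysed, correlation 0.6–0.8): 46–95% for alcohol alone and 3–73% for the three binary factors together. SD 8 and the 5-unit effect are the SAP's. Stratum shares, correlation and yes/no family history are assumptions.

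Two stronger conclusions are tempting but not supported. One is that false subgroup claims are likely in general: one in three under no effect is not likely, and the higher figures count a display pattern under assumed settings. The other is that the trial's main result is compromised: the primary ITT ANCOVA in SAP 6.2 does not depend on section 6.5.

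**What to change.** Amend SAP 6.5 before the analysis by arm:

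1. Fit the adjusted ANCOVA in the full ITT set, adding each factor in turn with its main effect and its treatment-by-factor term.
2. For the binary factors, report the interaction estimate, 95% CI and p-value. For alcohol, report a 3-df joint interaction test, since four bands have no single interaction estimate.
3. In the forest plot, show stratum estimates with 95% CIs and no p-values. State the levels of family history.
4. Label all subgroup analyses exploratory. State that four interaction tests at 5% carry about an 18% chance of at least one false signal. State also that power is low: about 26–37% for a 5-point difference in effect between two strata at 110 analysed, before any gain from baseline adjustment.
5. Reconcile SAP 6.5 (Secondary outcomes), which plans no subgroup analysis, with SAP 15.1 item (ii), which repeats subgroup analyses for key secondary outcomes.

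The cost is SAP wording and one results table. No extra data are needed.

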### Secondary outcomes

There is no pre-planned subgroup analysis for secondary outcomes.

## 6.6 Supplementary/ Additional Analyses and Outcomes

Any analyses further to the above and not specified in the analysis protocol will be exploratory in nature and it will be clearly labelled as a *post hoc* analysis and interpreted cautiously. If further analyses are carried out, a 0.01 significance levels will be used as evidence of statistical significance and 99% confidence intervals presented.

## 6.7 Harms

Adverse events are reported as a secondary outcome; see **Section 6.2 – Analysis methods (Safety analysis)** for further details.

## 6.8 Health Economics and Cost Effectiveness (where applicable)

*A summary from the protocol will be provided with reference to the relevant separate analysis plan (if applicable).*

The statistician is not undertaking this analysis.

## 6.9 Meta-analyses (if applicable)

There are no meta-analyses planned for the RIDD RCT.

## 7. VALIDATION OF THE PRIMARY ANALYSIS

To validate the primary outcome (nodule hardness) and key secondary outcomes a statistician not involved in the trial will independently repeat the analyses detailed in this SAP, by using different statistical software (if possible). The results will be compared and any discrepancies will be reported in the Statistical report (See OCTRU SOP STATS-005 Statistical Report). *If necessary, this will include derivation of the primary and key secondary outcomes from raw data.*

Repurposing anti-TNF for treating Dupuytren's disease (funded by Health Innovation Challenge Fund, Wellcome Trust)  
EudraCT Number: 2015-001780-40 and OCTRU Reference Number CTU0028

## 8. SPECIFICATION OF STATISTICAL PACKAGES

All analysis will be carried out using appropriate validated statistical software such as STATA, SAS, SPSS or R. The relevant package and version number will be recorded in the Statistical report and subsequent publications.

## 10. APPENDIX 1: GLOSSARY OF ABBREVIATIONS

ANCOVA	Analysis of Covariance
Anti-TNF	Anti-Tumour Necrosis Factor
CACE	Complier Average Causal Effect
CI	Chief Investigator
DD	Dupuytren's disease
DSMC	Data and Safety Monitoring Committee
EMA	European Medicines Agency
FDA	US Food and Drug Administration
IMP	Investigational Medical Products
ITT	Intention-to-treat
MHQ	Michigan Hand Outcomes Questionnaire
OCTRU	Oxford Clinical Trials Research Unit
PP	Per-protocol
RCT	Randomised Controlled Trial
TSC	Trial Steering Committee
TB	Tuberculosis
SAP	Statistical Analysis Plan

Repurposing anti-TNF for treating Dupuytren's disease (funded by Health Innovation Challenge Fund, Wellcome Trust)  
EudraCT Number: 2015-001780-40 and OCTRU Reference Number CTU0028

## 11. APPENDIX 2: RIDD PART 1; STATISTICAL ANALYSIS OUTLINE (FROM PROTOCOL)

During the dose response (**Part 1**), analysis will be carried out using data from all participants randomised to **Part 1**.

Descriptive statistics will be used to describe the demographics between the intervention groups for each dose. This difference in the mean between cases and controls will be reported with 95% confidence intervals for all continuous outcome variables. *P*-values will be reported to 3 decimal places.

The primary outcome measure for **Part 1** is expression of mRNA for  $\alpha$ -SMA. Expression will be quantified with PCR using the standard curve method using GADPH, B2M and PGK1 as housekeeping genes to normalise the samples.

The secondary outcome measures to be analysed include expression of mRNA for COL-1A1, COL-3A1, aherin 11 and levels of  $\alpha$ -SMA and collagen proteins, nodule size and nodule hardness.

For continuous variables, the difference in the means and the corresponding 95% confidence interval will be reported for each dose group and overall. For categorical variables, the number (and percentage) of participants in each category will be reported for each dose group and overall.

## 12. APPENDIX 3: SCORING GUIDELINES

### Michigan Hand Questionnaire

The Michigan Hand Outcomes Questionnaire (MHQ) is made up of six subscales. The raw scale score for each of the six scales is the sum of the responses of each scale item. The raw score is converted to a score ranging from 0-100. The response categories for the pain subscale are reversed since a higher score indicates more pain. For the other five scales, higher scores indicate better hand performance.

The score for the affected hand is obtained by selecting either the right or the left hand score. The affected hand will be the hand in which the injection is received. The hand for each item is listed in the MHQ and hand dominance is also recorded. The MHQ total score will be obtained by summing the scores for all six subscales (after reversing the pain scale) and then dividing the sum score by six.

Dealing with missing data: For the full MHQ, scores are only calculated if at least three of the six scales were complete. For overall hand function, pain and aesthetics scales, respondents must have had no more than two missing values for scores to be calculated. For any missing items, the average value of the present responses is imputed as the value for the missing response.

Details are given in **Table A1** below.

**Table A1:** Scoring rules for Michigan Hand Outcomes Questionnaire

Scale	Assessed for each hand separately?	Higher is better?	Calculated if:	Coding	Conversion formula
1. Overall hand function	Yes	Yes	$\leq 2$ missing items	Sum responses and convert to 0-100 scale	$(\text{Raw score}-25)/20*100$

Repurposing anti-TNF for treating Dupuytren's disease (funded by Health Innovation Challenge Fund, Wellcome Trust)  
EudraCT Number: 2015-001780-40 and OCTRU Reference Number CTU0028

Scale	Assessed for each hand separately?	Higher is better?	Calculated if:	Coding	Conversion formula
2. Activities of daily living (ADLs) in (i) Each hand, and (ii) Both hands	(i) Yes (ii) No	(i) Yes (ii) Yes	(i) ≤ 2 missing items (ii) ≤ 3 missing items	Sum responses and convert to 0-100 score. Then average the scores for (i) and (ii)	(i) (Raw score-25)/20*100 (ii) (Raw score-35)/28*100 Overall: (onehanded+twohanded)/2
3. Work performance	No	Yes	≤ 2 missing items	Sum responses and convert to 0-100 score	(Raw score-5)/20*100
4. Pain	Yes	No	≤ 2 missing items	Sum responses and convert to 0-100 score then calculate 100-raw score	If IV-A1=5 (right) or IV-B1=5 (left), pain score = 0 Otherwise, (Raw score-25)/20*100
5. Aesthetics	Yes	Yes	≤ 2 missing items	Sum responses and convert to 0-100 score	(Raw score-4)/16*100
6. Patient satisfaction with hand function	Yes	Yes	≤ 3 missing items	Sum responses and convert to 0-100 score	(Raw score-30)/24*100
Total	Yes	Yes	≥ 3 of the above 6 scales can be calculated	Average sum scores for above six scales	

[figure not shown]

Repurposing anti-TNF for treating Dupuytren's disease (funded by Health Innovation Challenge Fund, Wellcome Trust)  
EudraCT Number: 2015-001780-40 and OCTRU Reference Number CTU0028

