#### 6.3.1 Missing data

The number and proportion of individuals in the missing category for each secondary outcome variable will be reported, as well as reasons for missing if known.

Missing data distributions will be explored to assess whether the assumption that data are missing at random (MAR) is true. For patient-reported outcomes, participants for whom full questionnaires have not been completed will be excluded from the analysis of the corresponding outcome. For partially completed patient-reported outcomes, missing values will be imputed according to scoring guidelines for the relevant PROM (see **Appendix 3**).

During the analysis, techniques other than those suggested above may be used, for instance if data are not normally distributed or in the case of new techniques being developed in the meantime. No data will be considered spurious in the analysis since all data will be checked and cleaned before analysis.

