#### 6.3.2 Sensitivity analysis

All secondary outcomes will be subject to adjusted mixed effects regression analysis with time not included within the models as a random effect to assess the robustness of the conclusions to the timing of follow-up. The key secondary outcomes, MHQ and range of motion of the treated digit, will have a sensitivity analysis carried out on a PP basis to determine the effect of changes in procedures under which the intervention was received. CACE analysis will also be used to assess data quality and the impact of compliance on these key secondary outcome measures.

For those who have progressed to surgery, an analysis excluding participants where it is not known which digit was operated on will be undertaken.

For sensitivity analyses related to Covid-19, see **Appendix 6: Response to SARS-CoV-2 Pandemic (Covid-19)**.

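### The SAP allows an MHQ total from three of the six scales, but the only divisor it states is six, and no rule covers a wholly unscored scale

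*SAP*

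**What the plan says.** The MHQ is one of two outcomes given special standing in SAP section 6.3.2: "The key secondary outcomes, MHQ and range of motion of the treated digit". Its scoring is set out in SAP Appendix 3, which contains these rules:

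- **Scale scores.** For each scale, "The raw score is converted to a score ranging from 0-100".
- **Total, in the text.** It is obtained by "summing the scores for all six subscales (after reversing the pain scale) and then dividing the sum score by six".
- **Minimum for a total, in the text.** "For the full MHQ, scores are only calculated if at least three of the six scales were complete".
- **Total, in Table A1.** The condition is "≥ 3 of the above 6 scales can be calculated" and the coding entry is "Average sum scores for above six scales". The row gives no conversion formula.
- **Missing items.** "For any missing items, the average value of the present responses is imputed as the value for the missing response".

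In the body of the SAP, section 6.3.1 adds no rule for whole scales. It sends partial questionnaires back to the appendix: "For partially completed patient-reported outcomes, missing values will be imputed according to scoring guidelines for the relevant PROM".

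**The concern.** The formula in the text works only when all six scales are present. The minimum-scales rule explicitly allows a total when up to three are absent. For those questionnaires the SAP gives no value for the absent scale and no divisor other than six. A programmer who sums what is available and keeps the written divisor will lower the total of every partly scored questionnaire. One who averages the available scales will not.

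MHQ totals from all visits enter the mixed models of SAP section 6.3, with the baseline value as a covariate, so the choice affects both sides of the comparison over time. An unscored scale at follow-up would look like lost hand function, and one at baseline like a later gain. Partial completion is plausible: the protocol allows questionnaires by email or post (sections 8.6 and 8.8), and SAP Appendix 6 describes postal questionnaires during the pandemic.

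The gap also bears on quality control. SAP section 5.6 has summary scores checked by hand, and section 7 has an independent statistician repeat the key secondary analyses, from raw data if necessary. Both checks need a single rule.

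**Working it through.** The documents contain no worked MHQ total, so there is no stated figure to reproduce. The check applies the two candidate rules to the same questionnaire.

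**Inputs**
- Written divisor: 6 (Appendix 3, text).
- Number of scored scales k for which a total is allowed: 3 to 6 (Appendix 3, text and Table A1).
- Illustrative scale score: 80, the pilot mean MHQ score in early disease, with SD 17 (protocol section 4, Participant Reported Outcome Measures). Using 80 for every scale is an assumption, because no scale-level means are given. Each scale score is taken to be correctly converted to 0-100.

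**Rule A, written divisor kept:** total = (sum of k scored scales) / 6 = 80k/6.
**Rule B, mean of scored scales:** total = (sum of k scored scales) / k = 80k/k.

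| Scales scored (k) | Rule A | Rule B | A minus B | In pilot SDs (÷ 17) |
|---|---|---|---|---|
| 6 | 480/6 = 80.0 | 80.0 | 0 | 0 |
| 5 | 400/6 = 66.7 | 80.0 | -13.3 | -0.78 |
| 4 | 320/6 = 53.3 | 80.0 | -26.7 | -1.57 |
| 3 | 240/6 = 40.0 | 80.0 | -40.0 | -2.35 |

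The rules agree on complete questionnaires. Under Rule A each unscored scale removes one sixth of the scale score, here 80/6 = 13.3 points.

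**Effect on an arm mean.** The share f of partly scored questionnaires is not in the documents, so a range is assumed. The shift under Rule A is f × 13.3 with one scale missing and f × 40 with three missing.

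| Assumed f | One scale missing | Three scales missing |
|---|---|---|
| 2% | -0.3 | -0.8 |
| 5% | -0.7 | -2.0 |
| 10% | -1.3 | -4.0 |
| 20% | -2.7 | -8.0 |

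These are shifts in one arm at one visit. If both arms have the same share and pattern, and similar scores, the shifts largely cancel in the treatment contrast and what remains is extra variance.

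**The case against.** The strongest reply is that the divide-by-six sentence describes the complete case, where it is right. Missing data are treated in a separate paragraph that points to Table A1, and an average permitted from three scales reads naturally as the mean of those available. On that view the plan already intends the sensible rule and merely fails to spell it out.

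Much of this stands. A reader might infer that the plan always divides by six, or that an unscored scale counts as zero. Neither is stated anywhere; both come from carrying the complete-case formula over to incomplete questionnaires. A reader might also infer a systematic loss of hand function, but the error can run either way. Participants and outcome assessors are blinded (SAP section 3.2), and nothing in the documents suggests that blanks differ by arm. Nor should the 13.3-point effect of one missing scale be set beside the pilot difference between patients and controls (93 - 80 = 13): the first is an error in one person's score, the second a difference between group means. There is also no evidence on which scale would be skipped. The mean age of 63 in the background section describes surgical patients, not this trial's sample.

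The SAP has further protections. Section 6.3.1 excludes participants without full questionnaires from the relevant analysis, hand checks and independent repetition may expose a large drop, and secondary outcomes are only supportive under section 4.1.

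What the reply does not do is supply the missing rule. Table A1 still refers to six scales and gives no divisor for fewer, section 6.3.1 returns partial questionnaires to the same appendix, and giving no total would contradict the three-scale minimum.

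**Conclusion.** The point holds as a conflict between rules. The only divisor written for the MHQ total cannot properly be used with the three-scale minimum, and Table A1 suggests a different computation without defining it. The documents do not establish that unscored scales will be counted as zero.

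For an individual at 80 on every scored scale, the two readings differ by 13.3, 26.7 or 40.0 points with five, four or three scales scored. At arm level, assuming one missing scale in 2% to 20% of questionnaires, the shift would be about 0.3 to 2.7 points if six were kept as the divisor. That range rests on an assumed rate and a common scale score of 80. A bias between arms needs missingness that differs by arm; otherwise the consequence is mainly noise. The primary outcome is unaffected. Because the MHQ is a key secondary outcome and the correction is simple, it should be made.

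**What to change.** Before data lock, state in the text of Appendix 3 and in the Total row of Table A1 that the MHQ total is the sum of the scored scales (pain reversed) divided by the number of scales scored, calculated only when at least three are scored. Complete questionnaires are unaffected.

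Optionally, add a sensitivity analysis limited to participants with the same scales scored at baseline and follow-up, since a mean of available scales can still move when scales with different typical levels drop in or out.

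The cost is one sentence in the SAP, the matching table entry and one line of scoring code. No new data are needed.

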## 5.6 Reliability

Validation checks will be performed in order to check calculations and processes performed by a computer program by hand-checking a random sample of the largest of 5% of the available data or 20 patients. This will include if data have been imported and merged correctly. Prior to analysis, further validation checks will ensure that data are of the appropriate format, for example, within the maximum possible range of values. For example, when summary scores are calculated, these will be checked by hand calculations. Clarification will be sought by the trial office in the case of discrepancies.

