### Secondary outcomes

Nodule hardness over time: The change in hardness of the selected nodule for participants will also be assessed on each treatment at baseline, 3, 6, 9, 12, and 18 months after the first treatment.

Nodule size: Nodule size will be assessed using an ultrasound scan at baseline, 3, 6, 9, 12, and 18 months. Videos will also be obtained to ensure that the entire cross-section of the nodule has been recorded. For information on the translation of ultrasound images into measurement data for analysis please see **Appendix 4: Ultrasound images analysis**.

Grip strength: Measured using a Jamar meter (CE marked) at baseline, 3, 6, 9, 12, and 18 months. Previous studies of grip strength with patients with DD pre- and post-operatively have reported no significant change (Ball et al., 2013). It is anticipated that should a participant's nodule enlarge or become tender, then their grip strength might subsequently diminish.

Range of motion of the affected digit: Range of movement is the most frequently reported measure used to monitor DD progression and has demonstrated reliability, validity and sensitivity (Ball et al., 2013). Individual range of movement of finger joints will be measured using a goniometer at baseline, 3, 6, 9, 12, and 18 months post-first injection.

Michigan Hand Outcomes Questionnaire (MHQ): This is a patient-reported hand-specific measure that, unlike some other instruments, allows the user to separately score each hand at baseline, 3, 6, 9, 12, and 18 months. It contains six distinct scales that assess overall hand function, activities of daily living, pain, work performance, aesthetics, and patient satisfaction with hand function, with each scale being converted to a score ranging from 0 to 100 for reporting (see **Appendix 3**). The MHQ has been shown to have high test-retest reliability (Chung et al., 1998, Shauver & Chung, 2013) and internal consistency (Shauver & Chung, 2013), and has good construct validity depending on the condition assessed and good responsiveness (Shauver and Chung, 2013). It is a validated measure and has been shown to be sensitive to change when used to assess change in function over time in people with early DD (Broekstra, van den Heuvel, Lanting and Werker 2018) and improvement in hand function following hand surgery for established DD (Johnston et al., 2008, Herweijer et al., 2007). The MHQ was recommended following our systematic review of outcome measures for DD (Ball et al., 2013).

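### As printed, five of the seven MHQ conversion formulas in SAP Table A1 give −100 to 0 instead of the stated 0–100, and the plan does not say which repair applies

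*SAP*

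**What the plan says.** SAP Section 6.1 describes the MHQ as six scales, "with each scale being converted to a score ranging from 0 to 100 for reporting". Appendix 3 repeats this: "The raw score is converted to a score ranging from 0-100". It defines the raw score as the sum of the item responses.

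Table A1 in Appendix 3 gives the conversions, with daily activities split into a one-hand and a both-hands part, so there are seven formulas for six scales. Two contrasting cells are work performance, "Raw score-5)/20*100", and satisfaction, "Raw score-30)/24*100". Pain has its own rule, "If IV-A1=5 (right) or IV-B1=5 (left), pain score = 0 Otherwise, (Raw score-25)/20*100", and its coding instruction is "Sum responses and convert to 0-100 score then calculate 100-raw score". The appendix explains the reversal by noting that a higher pain score means more pain, and the table marks the total as higher is better.

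The number of items, the item codes and the direction of the responses are not stated for any scale.

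SAP Section 6.3.2 names MHQ as one of two key secondary outcomes, with its own per-protocol and CACE analyses. SAP Section 4.1 treats secondary outcomes as support for the primary conclusion only.

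**The concern.** A formula of the form (raw − c)/range × 100 runs from 0 to 100 only if c is the lowest possible raw score. In five of the seven cells c appears to be the highest possible raw score, with no minus sign in front to compensate. Those scales would then be zero or negative for every patient.

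What is at stake depends on the cause. A missing sign turns the scale round, so the MHQ total would add scales that point in opposite directions. A wrong constant only shifts the level. The two repairs run in opposite directions, so the choice should rest on the instrument and be made before anyone sees results by arm.

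**Working it through.** **Inputs.** The subtracted constants and divisors come from SAP Table A1. The 1–5 coding is an inference. For n items coded 1–5 the raw sum runs from n to 5n, with range 4n. Work (subtract 5, divide by 20) fits n = 20/4 = 5 with minimum 5. Aesthetics (subtract 4, divide by 16) fits n = 16/4 = 4 with minimum 4. The special pain rule also uses 5 as a response code.

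**Each formula at its lowest and highest raw score, 1–5 coding:**

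| Formula | Items (divisor/4) | Raw range | At lowest | At highest |
|---|---|---|---|---|
| Overall function | 20/4 = 5 | 5–25 | (5−25)/20×100 = −100 | (25−25)/20×100 = 0 |
| Daily activities, one hand | 20/4 = 5 | 5–25 | −100 | 0 |
| Daily activities, both hands | 28/4 = 7 | 7–35 | (7−35)/28×100 = −100 | 0 |
| Work | 20/4 = 5 | 5–25 | (5−5)/20×100 = 0 | (25−5)/20×100 = 100 |
| Pain, before reversal | 20/4 = 5 | 5–25 | −100 | 0 |
| Aesthetics | 16/4 = 4 | 4–20 | (4−4)/16×100 = 0 | (20−4)/16×100 = 100 |
| Satisfaction | 24/4 = 6 | 6–30 | (6−30)/24×100 = −100 | 0 |

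The stated 0–100 range is reproduced for two formulas and not for the other five.

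**Does another coding rescue the table?** With lowest code a and code width w, a divisor r implies r/w items and a raw minimum of a·r/w. The printed form gives 0–100 only if c/r = a/w. For work and aesthetics, c/r = 5/20 = 4/16 = 0.25. For the other five, c/r = 25/20 = 35/28 = 30/24 = 1.25. One coding cannot satisfy both. For example, 0–4 coding gives −125 to −25 for the five and −25 to 75 for work and aesthetics; 5–9 coding gives 0 to 100 for the five and 100 to 200 for work and aesthetics.

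**Pain.** Assume complete items, and read the reversal as 100 minus the converted score, which fits the order of the instruction.

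- Outside the rule, the first item is 1–4 and the others 1–5, so raw runs from 5 to 24.
- Converted: (5−25)/20×100 = −100 to (24−25)/20×100 = −5.
- Reversed: 100 − (−100) = 200 down to 100 − (−5) = 105.
- Under the rule: 100 − 0 = 100, if the rule's 0 is also reversed.

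So patients outside the rule score above those whom the rule treats as having no pain, on a total where higher is better.

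**Which repair fits pain?** At raw 25, (25−25)/20×100 = 0 with the sign changed, which agrees with code 5 scoring 0. Subtracting the minimum gives (25−5)/20×100 = 100, which does not. With the sign changed, patients outside the rule convert to 5 to 100 and reverse to 95 to 0. This points to a missing leading minus for pain, although the rule fixes the direction of the first pain item only. The other four formulas have no such clue.

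**Effect on the total.** Write F, A, W, P, E and S for correctly scored function, daily activities, work, reversed pain, aesthetics and satisfaction.

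- All five signs missing: F, A and S enter as −F, −A and −S, and pain as 200 − P. The total is (−F − A − S + 200 − P + W + E)/6, so four scales enter reversed and two enter correctly.
- Constant wrong only, on function, daily activities or satisfaction: the printed score is the true score minus 100 for every patient, and the between-arm difference on that scale does not change.

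**The case against.** The strongest objection is that the text was read from PDF and may have lost a leading minus. All five constants are exactly the raw maxima, one lost minus in each cell would put all five on 0–100, and that repair agrees with the pain rule. The minuses that survive are inside brackets or in front of numerals, as in the EQ-5D-5L worked example in the same appendix. None stands directly before a bracket, so their survival is weak evidence. This stands as a possibility that the source SAP would settle. It is not shown, and the formulas as they read are wrong.

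The second objection is that existing checks would catch the problem. SAP Section 5.6 tests whether data are "within the maximum possible range of values" and hand-checks summary scores. SAP Section 7 has key secondary outcomes repeated independently, and if necessary "this will include derivation of the primary and key secondary outcomes from raw data". The tables in SAP Appendix 5 show each MHQ component. Scales wholly at or below zero would probably be noticed. But none of these checks says whether the sign or the constant is to be corrected.

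Three stronger readings are tempting and not supported:

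- A reader might infer that the trial's MHQ effect is, or will be, reversed. The documents do not show the scoring code or say which cause applies. The Protocol's pilot MHQ means of 80 and 93 are plausible 0–100 scores, which fits a slip of notation at least as well as faulty scoring.
- A reader might infer that every patient outside the pain rule scores 105 or more. With the first pain item missing and the other four at 5, mean imputation gives raw 25 and a score of 100. If the reversal means 100 minus the raw sum, complete scores outside the rule are 100 − 24 = 76 to 100 − 5 = 95.
- A reader might infer that a total from three scales is halved because the text of Appendix 3 divides by six. That sentence concerns all six scales, and the table's total row speaks of an average. The two need aligning in wording, no more.

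**Conclusion.** The point holds as a wrong scoring rule as printed, and it should be fixed. Five of seven formulas give −100 to 0 on the coding the table implies, and no single coding puts all seven on 0–100. The pain figures (105 to 200, against 100 under the rule) hold for complete items, with the reversal applied to the converted score and also to the rule's 0.

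The size of any effect on the MHQ comparison cannot be given. If all five signs are missing, the total's treatment effect can shrink or reverse. If only a constant is wrong, the difference on that scale is unaffected; pain would need separate care, because patients under the rule are set to 0 and would not share the shift. The primary outcome is untouched.

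**What to change.** 1. Check the source SAP and the scoring code for a lost leading minus.
2. State the item count, item codes and response direction for each scale, and confirm the directions, including every pain item, against the instrument.
3. Correct the five formulas to (max − raw)/(max − min)×100 where low responses are better, or (raw − min)/(max − min)×100 where high responses are better. For pain, keep the conversion, the code-5 rule and the reversal consistent, and say whether the rule's 0 is itself reversed.
4. Confirm before unblinding that every scale lies in 0–100; the blinded analysis in SAP Section 3.6 is a natural place.
5. As a minor wording point, align the division by six in the text of Appendix 3 with the averaging in the total row of Table A1 for totals based on three to five scales.

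The cost is a few lines in Appendix 3 and a check of the scoring code. No new data are needed.
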